- Database of the Center for Clinical Trials (CCT) at the University of Maryland School of Medicine. Our CCT maintains a database of several thousand individuals who have expressed an interest in participating as research volunteers into clinical trials and other clinical research studies.
- Flyers on the University of Maryland Baltimore campus and notices in the campus newsletter. In the past, this approach has been very successful.

- The website of the University of Maryland Medical Center and the Division of Endocrinology, Diabetes and Nutrition.
- Newspaper advertisements. In addition, volunteers for this study will be recruited by advertisements in local and regional newspapers.

Initial screening for eligibility will be assessed by brief communication (telephone or in person) and include the following:

Inclusion criteria:

- Subjects will be overweight ($25 \text{ kg/m}^2 \leq \text{BMI} < 40 \text{ kg/m}^2$) but otherwise healthy men and women between the ages of 35 and 65 years who self-identify as (in NIH classification terms) White. As shown in a similar population in Section C4, the ability to show an improved insulin sensitivity in response to TZD treatment does not appear influenced by initial insulin sensitivity. Thus, no insulin sensitivity criteria will be applied.

Exclusion criteria:

- Diabetes (history of diabetes or as per screening tests)
- Medications that the investigator judges will make interpretation of the results difficult or increase the risk of participation (e.g., anticoagulants).
- Medical history that the investigator judges will make interpretation of the results difficult or increase the risk of participation (e.g., anemia, cardiac decompensation, intolerance to rosiglitazone, lidocaine or other agents used).
- Pregnancy
- Physical dimensions exceeding the limits of any equipment used

We will obtain written informed consent from all subjects. Further screening will include history, vital signs, physical exam, and blood tests. ***Please see Section E for detailed screening procedures and exclusion criteria.***

b. Metabolic testing:

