- Subcutaneous adipose tissue (3-5 g) will be removed from the abdominal region by aspiration with a 16-gauge needle under local anesthesia. A representative portion of the tissue will be handled as noted above. A portion of the tissue will be snap frozen in liquid nitrogen for subsequent RNA extraction and microarray analyses (see below). An aliquot of fresh adipose tissue will be transported immediately to [name] laboratory for the *in vitro* adipocyte studies (see below).

c. *Rosiglitazone intervention:*

Following the initial metabolic testing and sample acquisition, the subjects will initiate rosiglitazone therapy at 4 mg/day. At 4 weeks following the initiation, subjects will be evaluated by [name], Pharm.D., in order to ensure that there are no adverse effects from rosiglitazone therapy. Although liver dysfunction is much less common with rosiglitazone than troglitazone, we will measure serum ALT concentrations monthly. Medication compliance will be monitored using Trackcap (Medication Event Management Systems; Aprex Corp.), and by pill counting at each monthly visit. Frequent telephone contact will be maintained. If rosiglitazone is tolerated well after 4 weeks of treatment, the dose will be increased to the maximum dose of 8 mg (4 mg twice per day). We have chosen the maximum dose for rosiglitazone since to maximize the differences between responders and nonresponders. At each monthly visit, rosiglitazone drug levels will be measured to control for differences in drug when analyzing responsiveness.

d. *Metabolic testing after rosiglitazone therapy:*

After 12 weeks of rosiglitazone therapy, subjects will repeat metabolic testing identical to that described above taking place before the rosiglitazone intervention. Three months of therapy was chosen as the end point for the metabolic studies since by this time, rosiglitazone will have had its maximal effects on insulin sensitivity, the primary response outcome. Results of metabolic testing and clinical outcomes will be compared to the identical tests performed 12 weeks earlier (prior to the initiation to rosiglitazone) in the same subject.

e. *Analysis plan:*

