For the current study ($n = 75$ subjects) and TRIPOD studies ($n = 97$ subjects), we would have 80% or higher power to detect medium size effects (0.7 SD unit differences between means) across a wide range of allele frequencies (i.e., minor allele frequencies 0.1-0.5). For a putative subgroup of the current study with $n=38$, we would have 80% or higher power to detect large effect sizes (1.0-1.2) across the same allele frequencies. For the DPP ($n = 597$ subjects), we would have 80% or higher power to detect small size effects (0.3 SD unit differences between means) also across a wide range of allele frequencies. It is also worth noting that subjects to be recruited from this study will have mRNA levels measured, a very proximal phenotype that can be used as an additional outcome for the genetic association studies. One might expect a very large effect of an associated SNP on this particular phenotype.

E. HUMAN SUBJECTS RESEARCH

Protection of Human Subjects

1. Risks to the Subjects

a. Human subjects involvement and characteristics

Inclusion criteria

- Male or female who self-identifies as (in NIH classification terms) White.
- Age 35 - 65 years
- BMI 25 - 40 kg/m²

The age and BMI criteria were chosen to favor subjects with a relatively high likelihood of having insulin resistance and chronic inflammation, which makes intervention clinically meaningful.

Exclusion criteria

- History of diabetes (Doctor told pt. they had diabetes or pt. is taking diabetes medication)
- Fasting glucose value diagnostic for diabetes
- 2-h oral glucose tolerance test diagnostic for diabetes
- Medications that the investigator judges will make interpretation of the results difficult or increase the risk of participation (e.g., anticoagulants)
- Disease that the investigator judges will make interpretation of the results difficult or increase the risk of participation (e.g., anemia, cardiac decompensation, intolerance to rosiglitazone, lidocaine or other agents used)
- Pregnancy
- Physical dimensions exceeding the limits of any equipment used

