Screening will consist of medical history, vital signs, physical exam, and blood tests (a comprehensive chemistry profile, CBC, TSH, pregnancy test, 75 gram oral glucose tolerance test). Based upon this testing, subjects will be excluded if they have (1) stage III or greater congestive heart failure, symptomatic peripheral vascular disease, or stroke; (2) severe hypertension (BP>170/100); (3) anemia; (4) thyroid, pituitary, kidney or liver disease; (5) diabetes; (6) weight loss or gain of >5 kg in the previous six months; (6) hormone replacement therapy; (7) excessive use of caffeine (greater than three caffeinated drinks per day), or alcohol (greater than 3 ounces of liquor, or 3 x 4 ounce glasses of wine, or 3 x 12 ounce cans of beer per day); (8) use of medications that may affect glucose or lipid metabolism including beta blockers, thiazide diuretics, hypolipidemic agents, thyroid hormone, or

weight loss medications or formulas; (9) smoking >1/2 pack per day of cigarettes; and (10) pregnancy by urine testing.

Individuals with diabetes will be excluded because their metabolic control may vary, their likely use of multiple of multiple medications, and possible complications. From a statistical point of view, each source of variation can be regarded as an additional error term, requiring a much larger sample size for the same amount of power.

b. Sources of materials

Blood samples, urine samples, tissue samples, and results of physiological tests.

c. Potential risks

We expect no physical, psychological, social, or legal risks from a subject's participation in this protocol. Subjects who are screened, but not selected for participation for any reason will be referred to their primary health care provider for follow-up. Some of the procedures (DXA and CT scans) involve exposure to low doses of radioactivity; so pregnant women will be excluded from the study.

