We will heed the WARNINGS included in the rosiglitazone Product Information. We will monitor every four weeks for adverse events, including those mentioned in the Product Information, i.e., lower extremity edema and anemia. Patients will be questioned and examined at each visit regarding leg swelling. Rosiglitazone therapy will be decreased or discontinued in case of adverse events that are likely to be related to the drug. A complete blood count will be obtained at baseline and after 12 weeks to monitor for a decline in red blood cell concentrations as well as any other hematological derangements. Individuals with preexisting fluid retention or heart failure are ineligible for the study.

Although evidence indicates that rosiglitazone does not share the hepatotoxicity of troglitazone, we will monitor alanine transaminase every four weeks.

Subjects will be cautioned about the possibility of rosiglitazone to produce ovulation in some premenopausal women who might think themselves infertile. Adequate contraception in premenopausal women will be recommended.

Rosiglitazone will not be used in patients in whom it is CONTRAINDICATED (known hypersensitivity to the product or any of its components).

Genetic testing: Since the clinical relevance of the genetic testing is not yet proven, subjects will not be given any genetic information. If, in the future as a result of these studies or studies of others, gene variants that have clinical relevance are detected, all subjects who were genotyped will be contacted and first asked if they wish to know the result of their genotype analysis. If they do wish to be informed of their genotype, they will be informed by the investigators with the assistance of a genetics counselor, and with advice from an ethicist. However, subjects are given the option to decline all future genetic information when signing the consent form.

2. Adequacy of Protection Against Risks

a. Recruitment and informed consent

Written informed consent will be obtained from all subjects. The IRB approved consent form will be given to each subject, and informed written consent will be obtained by one of the investigators or a study coordinator following a personal interview with each subject. Subjects will be encouraged to read the consent form closely and the rationale, methods, potential risks and benefits of the interventions will be explained.

b. Protection against risks

Please see potential risks section above.

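### The screening list in Section E excludes heart failure only from stage III and omits fluid retention, although the same section makes both disqualifying at any stage

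*Combined protocol and SAP*

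**What the plan says.** The combined protocol and SAP deals with cardiac eligibility in four places.

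- **D.2.a, Subject recruitment and screening.** Volunteers are to be overweight but "otherwise healthy men and women between the ages of 35 and 65 years". A clause left to the investigator's judgement gives "anemia, cardiac decompensation, intolerance to rosiglitazone, lidocaine or other agents used" as examples of disqualifying history. The reader is then sent on: "Please see Section E for detailed screening procedures and exclusion criteria".
- **E.1.a, bulleted criteria.** The judgement clause is repeated with the same examples. The inclusion bullets cover race, age and BMI only; the requirement of good general health is not carried over from D.2.a.
- **E.1.a, screening paragraph.** "Screening will consist of medical history, vital signs, physical exam, and blood tests". On the basis of that testing, "subjects will be excluded if they have (1) stage III or greater congestive heart failure". The same item also covers symptomatic peripheral vascular disease and stroke, and further numbered items follow.
- **E.1.c, Rosiglitazone, (5) Use in non-diabetic individuals.** In the discussion of product warnings and monitoring: "Individuals with preexisting fluid retention or heart failure are ineligible for the study".

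**The concern.** The two explicit heart-failure rules in Section E differ in scope. One starts at stage III; the other has no lower limit and adds fluid retention. The narrower rule sits in the numbered list that a screener would naturally work from. The broader one appears once, inside the description of drug risks.

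This is a question of participant safety. Section B.2 describes fluid retention leading to edema and heart failure as a serious adverse effect that limits use of the class. Section E.1.c (4) reports lower-extremity edema in 5% of treated patients and links it to increased plasma volume. Section E.1.c (5) acknowledges that giving rosiglitazone to people without diabetes is off-label and that its safety has to be ensured. A person who already has mild heart failure or retained fluid is the person this exclusion exists to protect.

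**Working it through.** The protocol gives no figure to reproduce here. The check is a comparison of texts, followed by a short exposure calculation.

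**Step 1: scope of each statement**

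| Location | Heart failure | Fluid retention | Mandatory? |
|---|---|---|---|
| D.2.a and E.1.a judgement clause | Decompensation, as an example | Not named | No, investigator's judgement |
| E.1.a numbered list, item (1) | Stage III or greater | Not named | Yes |
| E.1.c (5) | Any, no stage limit | Any preexisting | Yes |

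The numbered list runs from (1) to (10) with (6) used twice, so it has 10 + 1 = 11 entries. Entries naming fluid retention or edema: 0.

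**Step 2: apply the two mandatory rules to three volunteers with no other listed condition**

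| Volunteer | E.1.a list | E.1.c (5) |
|---|---|---|
| Heart failure, stage III or greater | Excluded | Excluded |
| Heart failure below stage III | Not excluded | Excluded |
| Preexisting fluid retention, no heart failure | Not excluded | Excluded |

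The rules agree on the first volunteer and differ on the other two. Everyone caught by the stage III wording is also caught by E.1.c, so the threshold excludes nobody extra. All it can do is suggest that lower stages are acceptable.

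**Step 3: which text governs**

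D.2.a defers to Section E as a whole, and both statements are current Section E text. The difference therefore lies inside the governing section, and no order of precedence is stated.

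**Step 4: exposure of one person enrolled through the list wording**

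Inputs from D.2.c and D.2.d: "the subjects will initiate rosiglitazone therapy at 4 mg/day"; an evaluation at 4 weeks; then, if tolerated, 8 mg/day to week 12. Full adherence is assumed.

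- Duration: 12 × 7 = 84 days.
- Weeks 1–4: 28 days × 4 mg = 112 mg before the first scheduled evaluation. Telephone contact is planned in addition.
- Weeks 5–12: 84 − 28 = 56 days; 56 × 8 mg = 448 mg.
- Total: 112 + 448 = 560 mg.

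This is the ordinary planned dose for any participant. It shows what a misenrolled person could receive. It does not measure risk or the number affected.

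**The case against.** The strongest reply is that the statements do not contradict each other. Exclusions accumulate: the numbered list gives sufficient grounds for exclusion and does not declare everyone else eligible. The E.1.c sentence is plain eligibility text within the section to which D.2.a points. A person with mild heart failure is ineligible under the protocol as written, and enrolment would require a screener to read one paragraph alone.

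There are further protections:

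- D.2.a asks for people in otherwise good health, and the judgement clause allows exclusion of milder disease.
- The numbered list also excludes kidney and liver disease, recent weight change above 5 kg, beta blockers and thiazide diuretics. These items are mandatory and would remove some people with treated heart failure or fluid retention.
- On treatment, leg swelling is asked about and examined at each visit, the dose increase depends on tolerability, and the dose is cut or stopped for events likely to be drug-related.
- A monitoring board with clinical cardiology expertise meets quarterly (E.5).
- The protocol undertakes to heed the product warnings.

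Most of this stands. The stricter rule does apply, enrolment through the gap is unlikely, and the 560 mg figure is not a measure of harm. But the judgement clause is discretionary and its example does not clearly reach compensated heart failure. The other list items catch this group only in part. The history and physical exam may find the condition, yet item (1) tells the screener to act on heart failure only from stage III. On-treatment checks begin after exposure has started. None of these protections corrects the written threshold.

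**Conclusion.** The concern holds. E.1.a states a mandatory screening threshold that is narrower than the protocol's own rule in E.1.c, and it leaves out fluid retention altogether. It should be fixed, as a low-probability but safety-relevant inconsistency.

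The number of people affected cannot be derived from the documents. For one person, exposure would be 112 mg before the first scheduled evaluation and up to 560 mg over 84 days, assuming full adherence, tolerance at 4 weeks and no dose reduction. No sample size, power or analysis figure is affected. The conclusion rests on the wording of the two statements and on the assumption that a screener may work from the numbered list without the drug-risk text.

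**What to change.** In E.1.a, replace the heart-failure part of item (1) with: *heart failure of any stage or preexisting fluid retention*. Keep the rest of the item (peripheral vascular disease and stroke) unchanged. Assessment can rely on the history and physical exam already planned at screening. Leave the E.1.c sentence as it is. A matching bullet among the E.1.a exclusion criteria is optional.

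The cost is one wording change. No procedure is added, and at most a few volunteers are lost, all of whom E.1.c already makes ineligible. Sample size, power and analysis stay the same.

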Subjects who qualify for the study will then enter into the metabolic testing phase of the study. The identical metabolic testing will be performed before and after the 12-week rosiglitazone intervention. Methods for performing these tests have been standardized and are essentially identical to those being performed in our ongoing Pharmacogenetics of PPAR γ study. All testing will be performed at the University of Maryland General Clinical Research Center (see Letter from [name], GCRC Program Director).

Metabolic testing will include:

- Blood for fasting lipid profile and lipoprotein particle size, C-peptide, leptin, adiponectin, IL1 β , IL6, TNF α , hsCRP, SAA, adiponectin, and rosiglitazone concentrations.
- Imaging tests to determine total body fat and its distribution
 - Total body fat by dual energy x-ray absorptiometry (DEXA). We will use a Hologic QDR 4500 W scanner with Windows XP-based software allowing for region-of-interest analysis. The scans will be performed and analyzed by trained operators.
 - A single slice CT scan will be taken mid-way between the L4 and L5 lumbar vertebrae to determine intraabdominal fat area, subcutaneous fat area, and sagittal diameter. Another single slice CT scan will be taken at the thigh (halfway between the femoral head and the top of the patella) to assess limb fat and muscle area.
- Frequently sampled intravenous glucose tolerance test (IVGTT) to determine insulin sensitivity (using minimal modeling) and acute insulin response. As in our previous studies, data will be analyzed to provide parameters of insulin sensitivity and glucose effectiveness by the minimal model using a modified version of the computer program MINMOD.
- Muscle biopsy (100-250 mg) will be obtained under local anesthesia from the vastus lateralis. Connective tissue will be removed. A representative portion of the tissue will be formalin fixed,

paraffin embedded, sectioned, and stained with hematoxylin and eosin using standard histological methods. Slides will be examined visually to assess cell populations/tissue composition in order to ensure that morphologically similar tissue biopsies were sampled before and after rosiglitazone therapy. The remainder of the tissue will be snap frozen in liquid nitrogen for subsequent RNA extraction and microarray analyses (see below).

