Body composition: Dual energy x-ray absorptiometry (DXA) and CT scan entail exposure to radiation. The cumulative total body dose throughout the study is up to 0.015 rem from the DEXA scans and up to 0.040 rem from the CT scans. However, some organs will receive a larger dose from the CT scans: 0.092 rem to the ovaries (women only), 0.054 rem to the testes (men only), 0.060 rem to the bladder, and 0.058 rem to the rectum. Other organs and tissues will receive lesser radiation doses. These radiation doses are within institutional and federal guidelines for radiation exposure to research subjects and have never been associated with any definite adverse effects.

Phlebotomy and oral glucose tolerance test: The placement of intravenous needles and catheters may cause transient pain, and occasionally infection or bruising at the needle insertion site. The frequency and severity of these potential adverse events will be minimized by using sterile technique, universal precautions, and trained personnel. Blood volumes to be drawn are minimal, and therefore these tests are unlikely to cause anemia. For the oral glucose tolerance test, an indwelling catheter will be placed in an antecubital vein. Normal saline will be infused to maintain venous patency during the 2-h test. A solution containing 75 g of glucose is ingested by the fasting subject, which occasionally causes nausea.

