- The PI will be responsible for determining the causality of all AEs/SAEs subject to review by the UM-IRB and DSMB.
- The PI will be responsible for determining whether test results are "clinically significant" (CS) or "not clinically significant" (NCS). The PI will sign and date all lab reports as "CS" or "NCS".
- The PI and staff will be responsible for follow-up information on all AEs until resolution or an appropriate endpoint is reached.

The DSMB in concert with UMB-IRB will be responsible for reviewing all reports of SAEs which occur in this clinical trial and for determining whether any corrective actions need to be taken regarding: communication issues between the PI and the DSMB, management decisions of the PI and staff, whether protocol violations are congruous with patient welfare taking precedence over protocol, whether there are any issues among the research staff which need to be addressed, etc. The DSMB will be responsible to determine if the results of its review require a revision/modification of the RPN and/or the consent form.

6. Inclusion of women and minorities

Women are eligible for this research and will be actively recruited. We will halt recruitment of men or women if we reach more than 2/3 of either sex. To avoid analytical problems related to the inclusion of a highly stratified sample, only Caucasians will be eligible for Aim 1. However, because non-response to TZDs has never been associated with a particular race, we believe that the genes identified will be relevant to minorities as well, which we will be able to test in Aim 3, using banked DNA from the DPP and TRIPOD studies. Please see body of proposal for demographic description of the DPP and TRIPOD samples, which do not meet the requirements for listing in the Targeted/Planned Enrollment Table. The analysis strategy will address hypotheses related to sex and ethnicity/race. Please see enrollment table below.

TARGETED/PLANNED ENROLLMENT: Number of Subjects			
Ethnic Category	Sex/Gender		
	Females	Males	Total
Hispanic or Latino	0	0	0
Not Hispanic or Latino	37	38	75
Ethnic Category: Total of All Subjects *	37	38	75
Racial Categories			
American Indian/Alaska Native	0	0	0
Asian	0	0	0
Native Hawaiian or Other Pacific Islander	0	0	0
Black or African American	0	0	0
White	37	38	75
Racial Categories: Total of All Subjects	37	38	75

7. Inclusion of children

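### Pregnancy is excluded because of scan radiation but tested for only at screening, so nothing planned would detect an unrecognised pregnancy before the week-12 DXA and CT

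*Combined protocol and SAP*

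**What the plan says.** Section E.1.c (Potential risks) gives the reason for the exclusion: the DXA and CT scans "involve exposure to low doses of radioactivity; so pregnant women will be excluded from the study". Section E.1.a places pregnancy testing at screening. It lists a pregnancy test among the screening tests and excludes women found pregnant on urine testing.

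The scans belong to the metabolic testing in Section D.2.b: whole-body DXA, one CT slice at the thigh and one at the abdomen ("A single slice CT scan will be taken mid-way between the L4 and L5 lumbar vertebrae"). Section D.2.d schedules the whole battery again: "After 12 weeks of rosiglitazone therapy, subjects will repeat metabolic testing identical to that described above taking place before the rosiglitazone intervention".

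On-treatment checks appear in two places. Section D.2.c has monthly ALT, drug levels and pill counts, electronic cap monitoring and frequent telephone contact. The rosiglitazone part of Section E.1.c has adverse-event review and ALT every four weeks, examination for leg swelling, and a blood count: "A complete blood count will be obtained at baseline and after 12 weeks".

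The same part of Section E.1.c says subjects will be cautioned about the "possibility of rosiglitazone to produce ovulation in some premenopausal women who might think themselves infertile", and adds: "Adequate contraception in premenopausal women will be recommended". On dose, the body-composition paragraph of Section E.1.c says: "These radiation doses are within institutional and federal guidelines for radiation exposure to research subjects".

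**The concern.** The reason for the exclusion applies to each scan session, and there are two. It is checked once, at least 12 weeks before the second session. Between the check and the second exposure, participants take a drug that the plan says may restore fertility in women who believe themselves infertile. Those women are the least likely to suspect a pregnancy.

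The exclusion has no time limit, so a known pregnancy at week 12 is arguably already a bar to scanning. What the plan lacks is a way to find a pregnancy that nobody knows about. At stake is avoidable radiation to an early pregnancy, including a CT slice at L4–L5. Continued rosiglitazone exposure in that pregnancy is a second consequence. The study's estimates are not materially affected.

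**Working it through.** The plan gives no figure to reproduce here. The check sets its provisions side by side and then sizes the exposure.

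**Provisions**

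| Time | DXA and CT | Pregnancy test described |
|---|---|---|
| Screening (E.1.a) | No | Yes |
| Baseline testing (D.2.b) | Yes | No |
| Monthly visits on rosiglitazone (D.2.c, E.1.c) | No | No |
| Week-12 testing (D.2.d) | Yes | No |

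The second scan session has no pregnancy test before it other than the one at screening.

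**Women at risk**
- Planned women: 37 of 75 (Section E.6 enrolment table).
- Upper limit: Section E.6 says "We will halt recruitment of men or women if we reach more than 2/3 of either sex", which gives about 2/3 × 75 = 50.
- The eligible age range is 35–65 years, so premenopausal women can enrol. Their share is not stated; assume 30–60%.
- Low end: 37 × 0.30 = 11.1. High end: 50 × 0.60 = 30.

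**Expected conceptions.** Assume 0.1–1% per four-week cycle with contraception advised (not in the documents). Twelve weeks is three cycles.
- Over 12 weeks: 11.1 × 3 × 0.001 = 0.033, to 30 × 3 × 0.01 = 0.90.
- In the last four weeks, when a pregnancy is least likely to be recognised: 11.1 × 0.001 = 0.011, to 30 × 0.01 = 0.30.
- High end with the planned 37 women: 37 × 0.60 × 0.01 = 0.22 in the last four weeks, and 0.67 over 12 weeks.

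**Dose at week 12** (Section E.1.c, body composition)
- Cumulative whole-body dose: up to 0.015 (DXA) + 0.040 (CT) = 0.055 rem. Split equally between sessions (an assumption): 0.0275 rem.
- CT dose to the ovaries is stated as 0.092 rem. If cumulative, the week-12 share is 0.092 / 2 = 0.046 rem; if per session, it is 0.092 rem. The figure follows a sentence about cumulative dose, so 0.046 rem is the more natural reading.
- No uterine or fetal dose is given.

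**The case against.** The strongest reply is that this argues from silence. The document is a grant-style research plan without a visit-by-visit schedule. The consent form is not part of the text available for review, and Section D.2.b relies on standardised methods carried over from an ongoing study. A repeat test could be described elsewhere. The safety checks in Section E.1.c respond to product warnings and need not be exhaustive; monthly drug levels, for instance, appear only in Section D.2.c. That limits certainty, and the conclusion is confined to the available text. Even so, the plan names pregnancy testing at screening, names its on-treatment checks in two sections, and includes no pregnancy test in either.

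A second reply points to other safeguards: monthly visits, telephone contact, the duty in Section E.5 to report new clinical events, and a data and safety monitoring board meeting quarterly. These could bring a suspected pregnancy to light. They would not reveal one the woman is unaware of.

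A third reply is that the risk is tiny. Fewer than one conception is expected even at the assumed extremes. The doses are stated to be within guidelines and never linked to definite harm. This stands as a description of size. But the guideline statement concerns research subjects, and the plan already treats this same low dose as sufficient reason to exclude pregnant women.

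Finally, a single week-12 test comes after up to 12 weeks of drug exposure, and a urine test can miss a very early conception. Both points are right. The test narrows the gap without closing it.

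**Conclusion.** The concern holds. On the available text, a plan followed exactly as written would scan a woman with an unrecognised pregnancy at week 12, contrary to its own reason for excluding pregnant women. It should be fixed as a matter of participant safety; it is not an analysis flaw.

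The size is small: 0.03 to 0.9 expected conceptions in the whole trial, of which about 0.01 to 0.3 fall in the last four weeks. The top of each range combines the recruitment cap with the highest assumed rates. These numbers rest on the assumed premenopausal share and conception rate; the gap itself does not. Confidence is medium because the consent material could not be seen.

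**What to change.** Add to Section D.2.d, and to the screening and risk text in Section E.1, a urine pregnancy test in premenopausal women immediately before the post-treatment DXA and CT. Ideally, do the same before the baseline scans, since the interval from screening to baseline is not stated. If the test is positive: do not scan, stop rosiglitazone, and exclude that woman's post-treatment measurements from the response analysis. Testing at the existing monthly visits is an optional addition that would also limit drug exposure.

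The cost is about 11–30 urine tests for week 12, or 22–60 for both sessions, with no extra visits. The downsides are an occasional missing post-treatment scan and the chance of missing a very early conception. If a repeat test is already specified in the consent form or site procedures, stating it in the protocol is enough.
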